## 8 ANALYSIS CONVENTIONS

### 8.1 General principles

If 2 or more of the population sets as defined in the SAP coincide, presentations will only be prepared for 1 population.

All presentations will be done overall, i.e., for the single treatment group neridronic acid 400 mg. The data collected and derived in the trial will be presented in subject data listings.

Data collected in this trial will be summarized according to their nature as follows:

- Continuous variables: number of non-missing observations, arithmetic mean, standard deviation, minimum and maximum values, median and quartiles. If there are less than 5 observations, descriptive statistics will be presented based on the rules specified in Section 20.1.1.2.
- Categorical variables: absolute and relative frequencies. If not defined otherwise, the percentage denominator will be the number of subjects still in the trial at the respective time point in the analyzed population.
- Time-to-event variables: number of subjects, number of subjects with event, number of censored subjects, first quartile, median, and third quartile including 95% confidence interval. For calculating the survival estimate confidence interval (CI) bounds, the log-log transformed estimate of CI bounds will be used. In addition, Kaplan-Meier estimates and plots will be provided with the respective number at risk and the Kaplan-Meier estimates at the relevant time points together with the median and its 95% CI. Censoring mechanisms will be described in the respective section.

Medical terms (e.g., prior and concomitant diseases, adverse events) will be coded via Medical Dictionary for Regulatory Activities (MedDRA), and medications will be coded according to World Health Organization Drug Dictionary (WHO-DD).

[Table 1](#) shows the use of analysis sets in different analyses as defined in Section 9.

Table 1: Use of analysis sets

	Enrolled Set	Allocated Set	SAF	FAS	TCS	PD Set
Subject disposition	X					
Discontinuations		X				
Protocol deviations			X			
Demographics			X			
Other baseline characteristics			X			
Subject medical history			X			
Previous and concomitant medication			X			
Exposure			X			
Compliance			X			
Primary safety endpoint			X			
Secondary safety endpoint			X			
Secondary efficacy endpoints				X	X	
Adverse events			X			
Laboratory values			X			
Vital signs			X			
Twelve-lead ECG			X			
Physical examination			X			
Bone turnover markers						X
Health economics data				X		

ECG = electrocardiogram; FAS = Full Analysis Set; PD Set = Pharmacodynamic Set; SAF = Safety Set; TCS = Treatment Completers Set.

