# **10 DISPOSITION**

## **10.1 Subject disposition**

All presentations for subject disposition will be overall, i.e., for the single treatment group neridronic acid 400 mg.

For describing the subject disposition, the following populations will be summarized:

- Subjects enrolled.
- Subjects enrolled but not allocated and reason for non-allocation.
- Subjects allocated.
- Safety Set.
- Full Analysis Set.
- Treatment Completers Set (i.e., Treatment completers).
- Pharmacodynamic Set.
- Bone Biopsy Set.
- Bone Imaging Set.
- Trial completers.
- Follow-up completers.
- Subjects allocated and discontinued from the trial.
- Subjects allocated and discontinued from the trial per trial phase, i.e., during the treatment period, and during the follow-up period.
- Subjects who received 4 infusions, including partial infusions.
- Subjects allocated and discontinued IMP intake.
- Subjects allocated and discontinued IMP intake due to deterioration in renal function.

For subjects enrolled but not allocated and for the reasons for not being allocated, the percentage denominator will be the number of enrolled subjects. For all other calculations, the percentage denominator will be the number of allocated subjects.

In addition, an overview table will be prepared presenting the number of subjects enrolled, allocated, in the SAF, in the FAS, in the TCS, PD Set, Bone Biopsy Set, and Bone Imaging Set if applicable per country. Percentage calculation will be done in two ways:

- The denominator will be the number of all allocated subjects.
- The denominator will be the number of allocated subjects in the respective country.

Reasons for exclusion from the analysis populations will be summarized. The percentage denominator will be the number of subjects allocated.

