#### 13.2.1.2 Response to treatment

For each subject, the percentage change from baseline in current pain intensity will be calculated at each post-baseline visit (Visit 3 through Visit 11):

$$\%Change = \frac{Pain\ Intensity - Baseline}{Baseline} \cdot 100\%.$$

If the decrease is at least 30%, at least 50%, or at least 2 points on the NRS, the subject will be considered a responder for the respective threshold. If a subject shows a worsening or the pain intensity score is missing, the subject will not be considered a responder. This applies also to subjects with premature discontinuation where subsequent pain values are missing.

The percentage change from baseline, and the responder status (responder *Yes/No*) with respect to the 3 responder definitions will be presented in a subject data listing.

Descriptive summaries of the responder status will be presented by visit for each of the 3 responder definition. This includes the summary of the secondary responder endpoints, i.e., the response to treatment defined as at least 30%, at least 50% and at least 2 points on the NRS decrease from baseline at Week 12 (Visit 8) and Week 26 (Visit 9).

A graphical plot of the responder rates will be created by responder definition and visit.

For each of the 3 responder definitions, persistence of the treatment effect will be assessed by deriving a combined responder status for the following 3 time periods:

- Months 3 and 6 (Visit 8, and 9).
- Months 3, 6, and 9 (Visit 8, 9, and 10).
- Months 3, 6, 9, and 12 (Visit 8, 9, 10, and 11).

A subject is a combined responder if he/she is a responder at each of the visits mentioned in the definition of the respective time period. For the derivation of the combined responder status, the results of the individual visits are combined.

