#### **13.2.1.3 Patient Global Impression of Change**

The PGIC will be assessed at Visit 7 through Visit 11. Subjects respond to the question “Since the start of the trial, my overall status is:” with 1 of 7 possible responses (very much improved, much improved, minimally improved, no change, minimally worse, much worse, very much worse). A response of “very much improved” or “much improved” is generally regarded as a clinically important outcome. The response to treatment based on the PGIC will be derived by classifying subjects with outcome “very much improved” or “much improved” as responders, and subjects with other outcomes as non-responders. Subjects with missing PGIC score will be considered as non-responders.

All PGIC scores and the derived responder status will be presented in a subject data listing.

A descriptive summary of the categorical PGIC scores and the responder status will be generated by visit. This includes the summary of the secondary PGIC endpoints at Week 12 and Week 26.

A graphical plot of the distribution of the PGIC will be created by visit.

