### 15.1 Adverse events

All adverse events with start date/time after first IMP administration in a subject administered a trial treatment will be defined as treatment emergent adverse events (TEAE) irrespective of causal relationship.

A pre-treatment non-TEAEs is an adverse event starting in the pre-treatment period as defined in Section 8.2.2.

If there are partial dates or times, an adverse event will be considered treatment emergent unless the information available will clearly exclude it. Further details can be found in Section 20.1.6.1.

The causal relationship of TEAEs to IMP is categorized as follows:

Category	Assessment by investigator:
Related	certain probable/likely possible
Not related	unlikely not related
Unknown	unassessable/unclassifiable conditional/unclassified causal relationship is missing

A TEAE is considered to be ‘expected’ when the nature or intensity is consistent with the information in the neridronic acid investigator’s brochure. Otherwise, it is considered to be an ‘unexpected’ TEAE. Expectedness will be assessed by the sponsor.

The following overview tables will be generated overall, i.e., for the single treatment group neridronic acid 400 mg.

1. Summary of the number and percentage of subjects with at least 1:

- TEAE.
- Serious TEAE.
- Non-serious TEAE.
- Unexpected TEAE.
- Related TEAE.
- Related serious TEAEs.
- TEAE leading to discontinuation from IMP.
- TEAE leading to discontinuation from the trial.
- Deaths.

The percentage denominator will be the number of subjects.

2. Summary presenting the number of TEAEs per subject categorized as 0, 1, 2, 3, 4, 5, and >5.
3. Summary of the number and percentage of TEAEs for:
  - TEAEs.
  - Serious TEAEs.
  - Non-serious TEAEs.
  - Unexpected TEAE.
  - Related TEAEs.
  - Related serious TEAEs.
  - TEAE leading to discontinuation from IMP.
  - TEAE leading to discontinuation from the trial.

The percentage denominator will be the total number of TEAEs.

If more than 10 subjects discontinue the trial/IMP due to TEAE, the incidence and the incidence rate of TEAEs leading to discontinuation from the trial/from IMP will be summarized by SOC and PT.

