**20.1.1.7 Handling of missing values**

At each time point/visit, all subjects still in the trial are reported. Missing values will be taken into account as missing in the analysis. The number of observed values and the number of missing values must sum up to the number of subjects in the trial at the respective time point/visit.

Missing measurements/missing values are identified by the SDTM variable \*\*STAT=ND. If this variable is not recorded (it's a permissible variable) the missing values of \*\*ORRES should be used.

Unless otherwise specified in the SAP, missing values will not be imputed.

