**20.1.1.14 Handling of data from early termination visits**

Subjects who discontinue during the trial the before their Visit 11 will be requested to undergo an early termination visit with identical procedures to Visit 11. Procedures done at Visit 11 are listed in the schedule of events of the protocol.

If the last available visit is between Visit 2 and Visit 7, data from the early termination visit will be assigned to the next scheduled visit; otherwise data will be assigned to the nearest scheduled visit based on the trial day of the early termination visit and the planned visit day. The planned visit day is:

- Day 182 for Visit 9 (Week 26).
- Day 273 for Visit 10 (Week 39).
- Day 365 for Visit 11 (Week 52).

In case of equal distance to 2 scheduled visits, the earlier visit will be chosen. If the assigned visit already occurred before the early termination visit, the data will be assigned to the next scheduled visit.

Data from the early termination visit will be analyzed using the re-assigned visits.

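### Responder rates have no stated denominator, and the SAP's default would drop the discontinued subjects whom the responder rule counts as non-responders

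*SAP*

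**What the plan says.** SAP 8.1 sets a general rule for percentages of categorical variables: "If not defined otherwise, the percentage denominator will be the number of subjects still in the trial at the respective time point", taken within the population being analysed. SAP 20.1.1.7 follows the same logic for each visit: "The number of observed values and the number of missing values must sum up to the number of subjects in the trial" at that visit.

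The responder sections define status. SAP 13.2.1.2 treats a missing pain score as non-response and adds: "This applies also to subjects with premature discontinuation where subsequent pain values are missing". For persistence over Months 3 to 12 it says: "A subject is a combined responder if he/she is a responder at each of the visits mentioned in the definition". SAP 13.2.1.3 says: "Subjects with missing PGIC score will be considered as non-responders"; it does not mention discontinuation.

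None of these responder rules names a percentage denominator. SAP 13.2 names only the analysis sets (FAS and TCS), Protocol 1.5.3 places efficacy analyses on the FAS, and SAP 20.1.4 adds no efficacy-specific rule. Other sections do state a denominator, for example 10.1 ("For all other calculations, the percentage denominator will be the number of allocated subjects") and 15.1 ("The percentage denominator will be the number of subjects").

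For subjects who leave early, SAP 20.1.1.14 moves the early-termination assessment to a scheduled visit and says: "Data from the early termination visit will be analyzed using the re-assigned visits".

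**The concern.** Classing a subject as a non-responder affects a rate only if that subject is in the denominator. Two readings are open.

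1. **The 8.1 default applies.** Subjects who left the trial before the visit are not counted, and the discontinuation clause in 13.2.1.2 does nothing to the by-visit rates.
2. **13.2.1.2 is an exception to 8.1.** All FAS subjects are counted at every visit, and those who left count as failures.

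Subjects who remain in the trial but miss a score are non-responders either way. The difference lies only in those who left.

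The 30% and 50% pain responder rates and PGIC at Weeks 12 and 26 are secondary endpoints, and SAP 13.2 lists the 2-point response with them. A contract research organization will run the analysis from this SAP (Section 3), so two programmers could each follow the text and report different percentages. Under the default, response can also appear to rise over time merely because non-responders leave. That matters because the SAP plots responder rates by visit and assesses persistence of effect.

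**Working it through.** **Inputs.** N = 290, the approximate planned number (SAP 5.2), taken as the FAS. The documents give no dropout rate and no expected response rate for this trial, so there is no plan figure to reproduce and both are assumed. D is the number who left the trial before the visit, d = D/N, and R is the number of responders at the visit.

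**Formulas.**
- All-FAS rate = R/N.
- Default rate = R/(N − D).
- Ratio of the two = N/(N − D) = 1/(1 − d).
- Gap = p × D/N, where p is the response rate among those remaining.

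Subjects who left and have no score are never in R, so the default rate is the higher whenever D > 0 and R > 0.

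**Main case, p of about 40%, whole subjects.**

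| d | Remaining | R | Default | All FAS | Gap (points) | Factor |
|---|---|---|---|---|---|---|
| 5% | 276 | 110 | 110/276 = 39.9% | 110/290 = 37.9% | about 2 | 1.05 |
| 10% | 261 | 104 | 104/261 = 39.8% | 104/290 = 35.9% | about 4 | 1.11 |
| 20% | 232 | 93 | 93/232 = 40.1% | 93/290 = 32.1% | about 8 | 1.25 |
| 30% | 203 | 81 | 81/203 = 39.9% | 81/290 = 27.9% | about 12 | 1.43 |

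**Other response rates.** At d = 20%, 30% response gives 70/232 = 30.2% against 70/290 = 24.1%, and 50% response gives 116/232 = 50.0% against 116/290 = 40.0%. For 30% to 50% response the gap is 1.5 to 2.4, 3 to 5, 6 to 10 and 9 to 15 points at the four dropout levels.

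**Apparent trend.** Keep the same 104 responders and let only non-responders leave, so that 261 and then 232 subjects remain. The default rate goes from 104/261 = 39.8% to 104/232 = 44.8%. The all-FAS rate is 104/290 = 35.9% at both visits.

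**Early-termination scores.** At the visit to which a score is re-assigned, someone who has left can be a responder, which is why the factor is an upper limit. Take N = 290, D = 58 and R = 145, with k of the 145 responders being re-assigned early-termination cases. If all 58 are removed from numerator and denominator, the rate is (145 − k)/232, against 145/290 = 50.0% for all FAS:
- k = 0: 62.5%
- k = 15: 56.0%
- k = 29: 50.0%
- k = 40: 45.3%

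So at that one visit the rise can shrink, vanish or reverse, depending on how those subjects are handled. Later visits are not affected by their scores.

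**Combined responders.** Status spans two to four visits, while the 8.1 default refers to one time point. It therefore supplies no unique denominator for a combined-responder percentage.

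**The case against.** The best counter-argument is that specific text overrides general text. The 8.1 default yields to any other definition, 13.2.1.2 expressly carries non-response through discontinuation, and the by-visit summary follows directly. Together with the FAS as analysis set, this favours reading 2, where the gap is zero. That is plausible, but it does not settle the matter. The clause fixes status and does not name a denominator. It also keeps some effect under the default, because it still determines combined-responder status for subjects who leave after Week 12. The PGIC section has no such clause, so two parallel responder endpoints could end up with different denominators.

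Several narrower objections stand in part:

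- The explicit denominators in 10.1, 10.2 and 15.1 are weak evidence, since those are not by-visit tables. SAP 20.1.6.2 also restates the remaining-subjects count for categorical laboratory, vital-sign and ECG tables, and 13.2.1 does not. The inference runs both ways.
- Reading 20.1.1.7 with 20.1.1.14 suggests that a re-assigned score is an observed value, so the subject is counted at that visit. This is a reasonable inference, but it is not stated.
- Combined-responder status is defined for every subject. Only the denominator is missing.
- Only withdrawal from the trial matters. Protocol 9.3.2 asks subjects who stop IMP to stay in follow-up, and nothing in the documents predicts 20 to 30% dropout. Those rows are illustrations.
- Absolute counts are also reported, so a reader could recompute the all-FAS rate.

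These points limit the consequence. They do not supply the missing rule.

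**Conclusion.** The concern holds. The SAP names no denominator for its responder rates, and the only by-visit rule it does state removes the subjects whom 13.2.1.2 takes care to count as failures. If that default is followed, by-visit rates rise by a factor of up to 1/(1 − d). At 10% dropout and 40% response among those remaining, that is about 4 points. Under the exception reading it is nothing.

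The direction follows from the text, apart from a visit that receives re-assigned early-termination scores. The size rests on assumed dropout and response rates. This is an ambiguity with an unfavourable default, not a demonstrated error. It affects descriptive secondary endpoints only; no test and no primary result changes. It should be fixed before results are seen, so that the choice is not made afterwards.

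**What to change.** In SAP 13.2.1.2 and 13.2.1.3:

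- State that the denominator for every pain-responder, PGIC-responder and combined-responder rate is all subjects in the FAS (or the TCS, or the subgroup within that set) at every visit, and that this overrides 8.1 and 20.1.1.7.
- State that a subject whose early-termination score is re-assigned under 20.1.1.14 counts in both numerator and denominator at that visit.
- Label any rate based on observed cases only as supplementary.

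As an editorial point, note in SAP Section 13 that assigning non-responder status is an exception to its no-imputation sentence. SAP 20.1.1.7 already allows for exceptions, so this is only for clarity.

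The cost is a few sentences, with no new data or analysis. If the default had been intended, the reported rates will be somewhat lower.

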## 8.2 Definitions

### 8.2.1 Definition of subgroups

Two subgroups will be defined based on the duration of CRPS:

1. Subjects with duration  $\leq 2$  year from onset of symptoms suggestive of CRPS.
2. Subjects with duration  $>$  year from onset of symptoms suggestive of CRPS.

When subgroup analyses are specified, the analysis will be performed separately in each of the subgroups and overall.

**8.2.2 Further definitions**

Term	Definition
Baseline	
For this single-arm non-randomized trial, baseline is the last observation (scheduled or unscheduled) before first IMP administration, unless specified otherwise. In general, baseline is the value recorded at Visit 2.
 
For physical examinations, a general assessment will be done at Visit 1, and at all subsequent visits (scheduled or unscheduled) the change compared to the previous visit will be assessed.
 
For bone imaging assessments, a separate baseline visit must be scheduled during the enrollment period for subjects undergoing bone densitometry and magnetic resonance imaging procedures.

Early termination visit	Subjects who discontinue the follow-up period before their last planned visit should undergo an Early Termination Visit with procedures identical to Visit 11. If a subject discontinues then, the data recorded under Visit 11 in the eCRF are treated as data belonging to the Early Termination Visit.
Follow-up period	The follow-up period starts after the treatment period and ends at Visit 11.
Follow-up completers	Subjects completing Visit 11 in the follow-up period. Intermittent missed visits in the follow-up period are allowed and do not affect the follow-up completion status.
Investigational Medicinal Products (IMP)	Neridronic acid in the form of sodium neridronate hemi hydrate 108 mg for intravenous infusion (equivalent to 100 mg neridronic acid) supplied in 8 mL of excipients. The full contents of a single ampule or vial (8 mL) will be diluted in 500 mL normal saline and administered by slow intravenous infusion (240 minutes [maximum 260 minutes]) at Visit 2, Visit 3, Visit 4 and Visit 5, resulting in a total dose of neridronic acid 400 mg.
On-treatment-period	For the purpose of this trial, the on-treatment period starts at the first IMP administration (included) and continues until the date (included) when the subject leaves the trial, i.e., at Visit 11 for trial completers, and otherwise at the Early Termination Visit for discontinued subjects. This is based on the persistence in bone and potentially prolonged effect of neridronic acid.
Pooling of sites	
Individual sites will be combined to achieve pooled sites of similar size and with a sufficient number of subjects. Sites will be pooled by geographical region. The majority of sites are located in the United States of America (USA). Sites in the USA will be pooled in 4 regions based on United States (US) states:
 
 
• US North East: Connecticut (CT), Delaware (DE), Illinois (IL), Indiana (IN), Maine (ME), Maryland (MD), Massachusetts (MA), Michigan (MI), New Hampshire (NH), New Jersey (NJ), New York (NY), Ohio (OH), Pennsylvania (PA), Rhode Island (RI), Vermont (VT), and Washington D.C. (DC).
 
• US South East: Alabama (AL), Florida (FL), Georgia (GA), Kentucky (KY), North Carolina (NC), South Carolina (SC), Tennessee (TN), Virginia (VA), and West Virginia (WV).
 
• US Midwest: Arkansas (AR), Colorado (CO), Iowa (IA), Kansas (KS), Louisiana (LA), Minnesota (MN), Mississippi (MS), Missouri (MO), Montana (MT), Nebraska (NE), New Mexico (NM), North Dakota (ND), Oklahoma (OK), South Dakota (SD), Texas (TX), Wisconsin (WI), and Wyoming (WY).
 
• US West: Alaska (AK), Arizona (AZ), California (CA), Hawaii (HI), Idaho (ID), Nevada (NV), Oregon (OR), Utah (UT), and Washington (WA).
 
 
The sites in Europe will be pooled in one region, European Union (EU).

Pre-treatment-period	Before first IMP administration (excluded), i.e., the period between signature of the informed consent form and first administration of IMP.

Term	Definition
Subjects discontinued from treatment	Subjects permanently discontinued from IMP, i.e., subjects who stopped treatment prior to, or at any time during Visit 2, 3, 4, or 5.
Treated subjects	Subjects with at least 1 administration of IMP, including partial infusions.
Treatment period	The treatment period includes the four infusion visits starting at Visit 2 up to Visit 5. If a subject is permanently discontinued from treatment, the treatment period ends at the visit of the last infusion.
Treatment completers	Treated subjects who completed IMP administration according to the protocol, i.e., subjects who received the full dose of all 4 planned infusions of IMP. Treatment completers form the Treatment Completers Set defined below.
Trial completers	All subjects completing Visit 11 according to the protocol.

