## **1.3 Trial subjects – the population to be studied**

### **1.3.1 Inclusion criteria**

1. Informed consent signed.
2. Male or female subjects at least 18 years of age at Visit 1.
3. A diagnosis of CRPS according to the clinical diagnostic criteria recommended by the International Association for the Study of Pain (IASP; “Budapest clinical criteria”), assessed at Visit 1. Signs and symptoms of CRPS must apply to an affected limb (arm or leg) and must demonstrate asymmetry with respect to the contralateral limb.
4. Ongoing moderate to severe chronic pain, including a baseline current pain intensity score of  $\geq 4$  using an 11-point NRS, referring to the CRPS-affected limb, at Visit 2 (prior to dosing).
5. In stable treatment and follow-up therapy for CRPS for at least 1 month prior to allocation to treatment (Visit 2). Subjects must have failed trials of at least 2 treatments for CRPS, one of which must be a pharmacologic treatment (see Section 1.4.3).
6. Women of child-bearing potential must have a negative urine beta-human chorionic gonadotropin ( $\beta$ -HCG) pregnancy test at Visit 1 and must be using 2 forms of medically acceptable contraception, including at least 1 highly effective method of contraception with a low failure rate, defined as  $<1\%$  per year (e.g., oral contraceptives or intrauterine device), and a second medically acceptable method such as use of condoms with spermicide by their male partner. A barrier method alone is not acceptable. Highly effective methods of contraception must be used for at least 1 month prior to Visit 2 and for the duration of the trial.
7. Subjects must be able to communicate meaningfully, be able to differentiate with regard to location and intensity of the pain, and be able to answer the questions in the questionnaires used in this trial (assistance in filling out the questionnaires may be provided, if required due to motor or other impairment).

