f) Vitamin D and calcium supplements will be dispensed to subjects for use during the trial; subjects who are receiving appropriate doses of these supplements may continue without requirement for additional supplementation.

g) Compliance with inclusion and exclusion criteria must be confirmed before allocation to IMP, including pain score of at least 4 on the NRS.

h) Allocation must be performed using the interactive response technology system.

i) Subjects must be assessed prior to each infusion. This includes assessment for signs and symptoms of ocular inflammation, signs of proteinuria (see footnote p), and signs of dehydration. Subjects must be well hydrated prior to the start of infusions. Central safety laboratory data from the previous visit, in particular eGFR, must be evaluated prior to each infusion.

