#### **11.1.1.1 Visit 1 (Day -60 to Day -1)**

The following evaluations will be performed:

- Obtain written informed consent.
- Record demographic data.
- Record medical history (includes history of CRPS; for further details, see Section 1.6).
- The diagnosis of CRPS must be confirmed using the tablet computer at Visit 1 according to the clinical diagnostic criteria recommended by the IASP (Budapest clinical criteria) (for further details, see Section 12.2.3.1).
- Record dental history (for further details, see Section 1.6).
- Dispense calcium and vitamin D supplements (for further details, see Section 1.6).
- Record prior medications and therapies.
- Review inclusion/exclusion criteria.
- Record physical examination outcome.
- Record vital signs.
- Record triplicate 12-lead ECG.
- Record concomitant medications and therapies.
- Ask the subject to complete pain intensity assessments.
- Take blood for safety laboratory.
- Collect urine for central safety laboratory urinalysis.
- Perform a urine  $\beta$ -HCG pregnancy test (for women of child-bearing potential).
- Perform urine drugs of abuse testing.
- Provide subject trial card.
- Perform bone imaging (DXA and MRI will be performed in a subset of approximately 30 subjects [from US sites only]).
- Record adverse events (any events noted should be documented as medical history or as part of physical examination results).

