### **13.2.2 Sensitivity analysis**

Not applicable.

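### For current pain, one Visit 2 score is both the entry gate (at least 4) and the baseline, which biases the single-arm mean change and NRS responder rates modestly toward improvement; a Visit 1 sensitivity analysis would show by how much

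*SAP*

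**What the plan says.** Protocol 1.3.1, criterion 4, requires "Ongoing moderate to severe chronic pain, including a baseline current pain intensity score of" 4 or more, rated at Visit 2 before dosing. Protocol 1.6, footnote g, repeats it: "Compliance with inclusion and exclusion criteria must be confirmed before allocation to IMP, including pain score of at least 4 on the NRS".

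SAP 8.2.2 defines baseline: "baseline is the last observation (scheduled or unscheduled) before first IMP administration, unless specified otherwise". It adds: "In general, baseline is the value recorded at Visit 2". SAP 13.2.1.1 uses that baseline for the change in current pain at Visits 3 to 11 in the MMRM, both as the value subtracted and as a covariate. It calls for LS means with 95% CIs and a plot by visit. SAP 13.2.1.2 uses the same baseline for the 30%, 50% and 2-point responder definitions.

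Pain is also rated at Visit 1, between Day -60 and Day -1. Protocol 11.1.1.1 lists: "Ask the subject to complete pain intensity assessments". No numeric threshold is stated for that score, and it enters no planned change or responder calculation. The only use the text leaves open is in the listing and by-visit summary of current pain, or as a fallback baseline if the Visit 2 value were absent. SAP 13.2.2, on sensitivity analysis, reads "Not applicable".

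**The concern.** A single rating of pain at this moment carries day-to-day variation. A subject who happens to rate high on the day passes the gate, and one who happens to rate low does not. Among those admitted, the average Visit 2 error is therefore positive, later ratings do not share it, and the mean falls with no treatment effect. A randomised comparison would cancel this. Here change from the subject's own baseline is all there is for current pain.

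Baseline as an MMRM covariate does not help, because the LS means are evaluated over the gated cohort. What is at stake is the reading of the current-pain changes and NRS responder rates at Weeks 12 and 26, which are secondary efficacy endpoints. The primary safety endpoint and the sample size are unaffected.

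**Working it through.** **Inputs from the documents.** Gate of at least 4 on an integer 0 to 10 scale at Visit 2; Visit 2 as baseline; responder thresholds of 30%, 50% and 2 points; about 290 subjects (Protocol 1.5.1). The 290 rests on safety-database needs, so there is no planned effect size or power for pain to reproduce.

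**Assumptions, not in the documents.** Ungated mean 5.5 to 6.5, SD 2.0 to 2.3, correlation *r* between two single ratings 0.5 to 0.8, no true change over time, no selection at Visit 1, nobody missing.

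**Spurious mean fall.** With a gate on a normally distributed score,

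fall = (1 − *r*) × SD × φ(*a*) / (1 − Φ(*a*)), where *a* = (3.5 − mean) / SD.

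The cut is 3.5 because values from 3.5 upward round to 4.

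- Mean 6.5, SD 2.0, *r* 0.8: *a* = −1.50; 0.2 × 2.0 × 0.1295 / 0.9332 = 0.056.
- Mean 6, SD 2.0, *r* 0.7: *a* = −1.25; 0.3 × 2.0 × 0.1826 / 0.8944 = 0.12.
- Mean 5.5, SD 2.3, *r* 0.5: *a* = −0.87; 0.5 × 2.3 × 0.2733 / 0.8077 = 0.39.

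Simulation with ratings rounded and clipped to 0 to 10 gives 0.06, 0.13 and 0.40 for these cases. In the same gated subjects, a Visit 1 reference gives 0.00 throughout, and the mean of Visits 1 and 2 halves the artefact. More extreme inputs widen the Visit 2 fall to between 0.01 (mean 7, SD 1.5, *r* 0.8) and 0.58 (mean 5, SD 2.5, *r* 0.5).

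**Against the width of the CI.** For mean 6, SD 2.0, *r* 0.7, the change has SD 1.536, so SE = 1.536 / √290 = 0.090. A fall of 0.131 is then about 1.5 SE, and a simple 95% CI for the mean change would lie wholly below zero about 31% of the time with no effect, against 2.5% nominal. Over mean 5 to 6.5 at SD 2 and *r* 0.5 to 0.8, that chance runs from 13% to 95%.

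**Responders with no true change.** Example with mean 6, SD 2.3, *r* 0.7:

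| Reference | Mean change | 30% responders |
|---|---|---|
| Visit 2 (gated) | −0.19 | 13.8% |
| Visit 1 | 0.00 | 12.1% |
| Mean of Visits 1 and 2 | −0.09 | 10.9% |

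The gate's share is the first row less the second: 13.8 − 12.1 = 1.7 percentage points. The other 12.1% is visit-to-visit noise, which a Visit 1 reference does not remove. The third row is lowest, although half gated, because averaging two ratings cuts noise; it does not measure the gate effect.

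Over the assumed range the gate adds about 0.5 to 3.4 points to 30% responders and 0.3 to 2.4 points to 50% responders. Of 290 subjects that is about 1 to 10 (0.005 × 290 to 0.034 × 290) and 1 to 7 (0.003 × 290 to 0.024 × 290).

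**If Visit 1 is informally screened at 4 or more.** With mean 6, SD 2.0, *r* 0.6, the Visit 1 and Visit 2 references both give −0.14, so the remedy loses its advantage. The data would reveal this: without such a screen, 3% to 16% of treated subjects should have a Visit 1 score below 4 (mean 5 to 6.5, SD 2, *r* 0.5 to 0.8).

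**The case against.** The strongest reply is that efficacy here is exploratory. Protocol 1.5 plans no inferential testing, and Protocol 8.1 asks for caution because there is no comparator. That limits the harm and stands. But the caution names only the missing comparator, not selection on the baseline score, and SAP 13.2.1.1 still reports CIs and a plot that readers will use.

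The second reply also stands in part: Visit 1 is not a clean reference. It can fall 60 days before dosing, while criterion 5 asks for stable therapy only for 1 month before Visit 2 and exclusion 12 bars certain procedures only within 6 weeks before Visit 2. A Visit 1 score may predate a therapy change. Eligibility is also reviewed at Visit 1, and criterion 4 speaks of ongoing moderate to severe pain, so some selection there is possible.

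Three stronger readings are tempting, and the documents do not support them:

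- That all efficacy results are inflated. PGIC has no baseline (Protocol 12.4.2). BPI, the other scales, and worst and average pain are not themselves gated.
- That the 32.5% placebo response cited in Protocol 6.3 (at least 50% decrease at 40 days) measures the problem. Applied to 290 it would be about 94 subjects (0.325 × 290), against the 1 to 7 attributable to the gate above. That figure reflects all improvement without drug, which only a control arm could address.
- That scores are pushed up to reach 4. Treatment is open-label, and Protocol 9.1 bars re-enrollment after failing the pain level, so an incentive exists. Nothing in the documents allows its size to be estimated.

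**Conclusion.** The point holds for current pain. One Visit 2 rating is gate and baseline, the direction of the bias is known, the MMRM covariate does not remove it, and no planned analysis shows its size. Under the assumed inputs it is small to moderate: 0.06 to 0.40 NRS points on the mean change, and a few percentage points at most on the 30% and 50% responder rates. The figures rest on assumed mean, SD and correlation, a stable condition, and no selection at Visit 1. The gap is worth closing because the data are already collected, but it does not make the Visit 2 baseline wrong as the main choice.

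**What to change.** In SAP 13.2.2, replace the present entry with a sensitivity analysis of current pain:

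1. Re-derive the Week 12 and Week 26 change, the MMRM visit means and the three NRS responder rates with the Visit 1 score as reference. Secondarily, use the mean of Visits 1 and 2, noting that this only halves the gate effect.
2. Count a Visit 1 score of 0 as a non-responder for the percentage definitions, since percentage change is then undefined.
3. Tabulate the Visit 1 score distribution, including the share below 4, and the change from Visit 1 to Visit 2 with its 95% CI. With no Visit 1 selection and stable pain, that untreated rise estimates the later spurious fall.
4. Repeat items 1 and 3 in subjects with no recorded change in CRPS medication or therapy between Visits 1 and 2.
5. State that therapy changes and informal Visit 1 selection limit interpretation.

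Keep Visit 2 as the main baseline. The cost is SAP wording and some extra analysis work with existing programs; no new data are needed. The reported effect may look slightly smaller.
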